10.3.3.3. Other Exploratory Analyses

The exploratory graphics described below will be created.

- Scatter plots of mean weekly daprodustat dose over the EP vs. the percent time within the Hgb target range during the EP
- Scatter plots of mean weekly three-times weekly daprodustat dose over 52 weeks vs. mean Hgb over the 52-week treatment period
- Boxplots of mean weekly three-times weekly daprodustat dose, while on study treatment for participants without MACE, and before the event for participants with MACE or combined safety endpoint
- Boxplots of Cmax of three-times weekly dosed daprodustat extrapolated to daprodustat dose at PK sample multiplied by the daprodustat dose at the time of MACE or combined safety endpoint (or end of study if no endpoint) by participants with or without MACE or combined safety endpoint

10.3.4. Interim Analyses

The IDMC will periodically receive unblinded safety reports containing clinical endpoints (whether adjudicated or pending adjudication) and SAEs, from an independent Statistical Data Analysis Center (SDAC) while Phase 3 studies with daprodustat are ongoing. The IDMC may recommend stopping this study for safety at any time.

There are no plans to evaluate interim data for the purposes of stopping based on Hgb efficacy data.

Further details will be specified in the IDMC charter and RAP.

12. APPENDICES

12.1. Appendix 1: Abbreviations and Trademarks

Abbreviations

AE	Adverse event
AESI	Adverse event of special interest
ALT	Alanine transaminase
ANCOVA	Analysis of Covariance
ANSM	L'Agence nationale de sécurité du médicament et des produits de santé
AST	Aspartate transaminase
BP	Blood pressure
CEC	Clinical Events Committee
CHF	Congestive Heart Failure
CI	Confidence interval
CKD	Chronic kidney disease
CNIL	Commission Nationale de l'Informatique et des Libertés
CPK	Creatine phosphokinase
CRA	Clinical Research Assistant
CT	Computed tomography
CTR	Clinical Trials Register
CV	Cardiovascular
DBP	Diastolic blood pressure
ECG	Electrocardiogram
eCRF	Electronic case report form
EDW	Estimated dry weight
EP	Evaluation period
EPO	Erythropoietin
ESA	Erythropoiesis-stimulating agent
FDA	Food and Drug Administration
FSH	Follicle stimulating hormone
GCP	Good Clinical Practice
GCSP	Global Clinical Safety and Pharmacovigilance
GI	Gastrointestinal
GSK	GlaxoSmithKline
HbA1c	Glycated hemoglobin
HD	Hemodialysis
HDL-c	High density lipoprotein-C
HDPE	High density polyethylene
Hgb	Hemoglobin
HIF	Hypoxia-inducible factor
HIF-PHI	Hypoxia inducible factor prolyl hydroxylase inhibitor
HR	Heart rate
HRT	Hormone replacement therapy

hsCRP	High sensitivity C-reactive protein
IB	Investigator's Brochure
ICH	International Council for Harmonization
IDMC	Independent Data Monitoring Committee
IEC	Independent Ethics Committee
iPTH	Intact parathyroid hormone
IRB	Institutional Review Board
IRT	Interactive Response Technology
ITT	Intent-to-treat
IV	Intravenous
KDIGO	Kidney Disease Improving Global Outcomes
KDOQI	Kidney Disease Outcomes Quality Initiative
LDH	Lactate dehydrogenase
LDL-C	Low density lipoprotein-C
M2	GSK2391220, M2 metabolite of GSK1278863 (daprodustat)
M3	GSK2531403 and GSK2506104, stereoisomers of the M3 chiral metabolite of GSK1278863 (daprodustat)
M4	GSK2487818, M4 metabolite of GSK1278863 (daprodustat)
M5	GSK2531399 and GSK2506102, stereoisomers of the M5 chiral metabolite of GSK1278863 (daprodustat)
M6	GSK2531398 and GSK2531407, stereoisomers of the M6 chiral metabolite of GSK1278863 (daprodustat)
M13	GSK2531400 and GSK2531401, stereoisomers of the M13 chiral metabolite of GSK1278863 (daprodustat)
MACE	Major adverse cardiovascular event
MAP	Mean arterial pressure
MCH	Mean corpuscular hemoglobin
MCHC	Mean corpuscular hemoglobin concentration
MCV	Mean corpuscular volume
MedDRA	Medical Dictionary for Regulatory Activities
MI	Myocardial infarction
MRI	Magnetic resonance imaging
MSDS	Material Safety Data Sheet
NYHA	New York Heart Association
PASP	Pulmonary artery systolic pressure
PD	Pharmacodynamic
PEG	Polyethylene glycol
PGI-C	Patient Global Impression of Change
PGI-S	Patient Global Impression of Severity
PHI	Prolyl hydroxylase inhibitor
PK	Pharmacokinetic
PP	Per protocol
PPD	Pharmaceutical Product Development, LLC
PRBC	Packed red blood cells

PSRAE	Possible Suicidality Related Adverse Events
QC	Quality control
QT	Q-T interval
QTc	Q-T interval corrected for heart rate
QTcB	Bazett's correction of QT interval
RAP	Reporting and Analysis Plan
RBC	Red blood cell
RDW	Red blood cell distribution width
rhEPO	Recombinant human erythropoietin
SAE	Serious adverse event
SBP	Systolic blood pressure
SC	Subcutaneous
SD	Standard deviation
SDAC	Statistical Data Analysis Center
SRM	Study Reference Manual
TIBC	Total iron binding capacity
TSAT	Transferrin saturation
U	Units
UIBC	Unsaturated iron binding capacity
ULN	Upper limit of normal
US	United States
VEGF	Vascular endothelial growth factor
WBC	White blood cells

Trademark Information

Trademarks of the GlaxoSmithKline group of companies
NONE

Trademarks not owned by the GlaxoSmithKline group of companies
Epogen
HemoCue
MedDRA

12.2. Appendix 2: Study Governance Considerations

12.2.1. Regulatory and Ethical Considerations

- This study will be conducted in accordance with the protocol and with:
 - Consensus ethical principles derived from international guidelines including the Declaration of Helsinki and Council for International Organizations of Medical Sciences (CIOMS) International Ethical Guidelines
 - Applicable ICH Good Clinical Practice (GCP) Guidelines
 - Applicable laws and regulations
- The protocol, protocol amendments, ICF, Investigator Brochure, and other relevant documents (e.g., advertisements) must be submitted to an IRB/IEC by the investigator and reviewed and approved by the IRB/IEC before the study is initiated.
- Any amendments to the protocol will require IEC/IRB approval before implementation of changes made to the study design, except for changes necessary to eliminate an immediate hazard to study participants.
- The investigator will be responsible for the following:
 - Providing written summaries of the status of the study to the IRB/IEC annually or more frequently in accordance with the requirements, policies, and procedures established by the IRB/IEC
 - Notifying the IRB/IEC of SAE or other significant safety findings as required by IRB/IEC procedures
 - Providing oversight of the conduct of the study at the site and adherence to requirements of 21 CFR, ICH guidelines, the IRB/IEC, European regulation 536/2014 for clinical studies (if applicable), and all other applicable local regulations

12.2.2. Financial Disclosure

Investigators and sub-investigators will provide the sponsor with sufficient, accurate financial information as requested to allow the sponsor to submit complete and accurate financial certification or disclosure statements to the appropriate regulatory authorities. Investigators are responsible for providing information on financial interests during the course of the study and for 1 year after completion of the study.

12.2.3. Informed Consent Process

- The investigator or his/her representative will explain the nature of the study to the participant or his/her legally authorized representative and answer all questions regarding the study.

- Participants must be informed that their participation is voluntary. Participants or their legally authorized representative will be required to sign a statement of informed consent that meets the requirements of 21 CFR 50, local regulations, ICH guidelines, Health Insurance Portability and Accountability Act (HIPAA) requirements, where applicable, and the IRB/IEC or study center.
- The medical record must include a statement that written informed consent was obtained before the participant was enrolled in the study and the date the written consent was obtained. The authorized person obtaining the informed consent must also sign the ICF.
- Participants must be re-consented to the most current version of the ICF(s) during their participation in the study.
- A copy of the ICF(s) must be provided to the participant or the participant's legally authorized representative.
- Participants who are rescreened are required to sign a new ICF.

12.2.4. Data Protection

- Participants will be assigned a unique identifier by the sponsor. Any participant records or datasets that are transferred to the sponsor will contain the identifier only; participant names or any information which would make the participant identifiable will not be transferred.
- The participant must be informed that his/her personal study-related data will be used by the sponsor in accordance with local data protection law. The level of disclosure must also be explained to the participant.
- The participant must be informed that his/her medical records may be examined by Clinical Quality Assurance auditors or other authorized personnel appointed by the sponsor, by appropriate IRB/IEC members, and by inspectors from regulatory authorities.

12.2.5. Committees Structure

In addition to GSK, medical governance will also be provided by the following independent committees. Additional information about each committee is included in the respective committee charter which is available upon request.

12.2.5.1. Independent Data Monitoring Committee

An IDMC will be utilized in this study to ensure external objective review of safety and efficacy data in order to protect the ethical and safety interests of participants and to protect the scientific validity of the study. The schedule of any planned interim analysis and the analysis plan for IDMC review is described in the charter.

12.2.5.2. Clinical Events Committee

An external independent Clinical Events Committee (CEC) blinded to study treatment allocation will adjudicate all events reported during this study that constitute events of MACE, thromboembolic events and hospitalization for heart failure, as outlined in

Section 9.2.5. Further details are contained within the CEC Charter (available on request).

12.2.6. Publication Policy

- The results of this study may be published or presented at scientific meetings. If this is foreseen, the investigator agrees to submit all manuscripts or abstracts to the sponsor before submission. This allows the sponsor to protect proprietary information and to provide comments.
- The sponsor will comply with the requirements for publication of study results. In accordance with standard editorial and ethical practice, the sponsor will generally support publication of multicenter studies only in their entirety and not as individual site data. In this case, a coordinating investigator will be designated by mutual agreement.
- Authorship will be determined by mutual agreement and in line with International Committee of Medical Journal Editors authorship requirements.

12.2.7. Dissemination of Clinical Study Data

- Where required by applicable regulatory requirements, an investigator signatory will be identified for the approval of the clinical study report. The investigator will be provided reasonable access to statistical tables, figures, and relevant reports and will have the opportunity to review the complete study results at a GSK site or other mutually-agreeable location.
- GSK will also provide the investigator with the full summary of the study results. The investigator is encouraged to share the summary results with the study participants, as appropriate.
- GSK will provide the investigator with the randomization codes for their site only after completion of the full statistical analysis.
- The procedures and timing for public disclosure of the results summary and for development of a manuscript for publication will be in accordance with GSK Policy.
- A manuscript will be progressed for publication in the scientific literature if the results provide important scientific or medical knowledge.

12.2.8. Data Quality Assurance

- All participant data relating to the study will be recorded on printed or electronic CRF unless transmitted to the sponsor or designee electronically (e.g., laboratory data). The investigator is responsible for verifying that data entries are accurate and correct by physically or electronically signing the CRF.
- The investigator must maintain accurate documentation (source data) that supports the information entered in the CRF.

- The investigator must permit study-related monitoring, audits, IRB/IEC review, and regulatory agency inspections and provide direct access to source data documents.
- The sponsor or designee is responsible for the data management of this study including quality checking of the data.
- Study monitors will perform ongoing source data verification to confirm that data entered into the CRF by authorized site personnel are accurate, complete, and verifiable from source documents; that the safety and rights of participants are being protected; and that the study is being conducted in accordance with the currently approved protocol and any other study agreements, ICH GCP, and all applicable regulatory requirements.
- Records and documents, including signed ICF, pertaining to the conduct of this study must be retained by the investigator for 25 years from the issue of the final Clinical Study Report (CSR)/ equivalent summary unless local regulations or institutional policies require a longer retention period. No records may be destroyed during the retention period without the written approval of the sponsor. No records may be transferred to another location or party without written notification to the sponsor.

12.2.9. Source Documents

- Source documents provide evidence for the existence of the participant and substantiate the integrity of the data collected. Source documents are filed at the investigator's site.
- Data reported on the CRF or entered in the eCRF that are transcribed from source documents must be consistent with the source documents or the discrepancies must be explained. The investigator may need to request previous medical records or transfer records, depending on the study. Also, current medical records must be available.
- Definition of what constitutes source data can be found in the study specific monitoring plan.

12.2.10. Study and Site Closure

GSK or its designee reserves the right to close the study site or terminate the study at any time for any reason at the sole discretion of GSK. Study sites will be closed upon study completion. A study site is considered closed when all required documents and study supplies have been collected and a study-site closure visit has been performed.

The investigator may initiate study-site closure at any time, provided there is reasonable cause and sufficient notice is given in advance of the intended termination.

Reasons for the early closure of a study site by the sponsor or investigator may include but are not limited to:

- Failure of the investigator to comply with the protocol, the requirements of the IRB/IEC or local health authorities, the sponsor's procedures, or GCP guidelines

- Inadequate recruitment of participants by the investigator
- Discontinuation of further study treatment development

12.3. Appendix 3: Adverse Events: Definitions and Procedures for Recording, Evaluating, Follow-up, and Reporting

12.3.1. Definition of AE

AE Definition

- An AE is any untoward medical occurrence in a clinical study participant, temporally associated with the use of a study treatment, whether or not considered related to the study treatment.
- NOTE: An AE can therefore be any unfavorable and unintended sign (including an abnormal laboratory finding), symptom, or disease (new or exacerbated) temporally associated with the use of a study treatment.

Events Meeting the AE Definition

- Any abnormal laboratory test results (hematology, clinical chemistry, or urinalysis) or other safety assessments (e.g., ECG, radiological scans, vital signs measurements), including those that worsen from baseline, considered clinically significant in the medical and scientific judgment of the investigator (i.e., not related to progression of underlying disease).
- Exacerbation of a chronic or intermittent pre-existing condition including either an increase in frequency and/or intensity of the condition.
- New conditions detected or diagnosed after study treatment administration even though it may have been present before the start of the study.
- Signs, symptoms, or the clinical sequelae of a suspected drug-drug interaction.
- Signs, symptoms, or the clinical sequelae of a suspected overdose of either study treatment or a concomitant medication. Overdose per se will not be reported as an AE/SAE unless it is an intentional overdose taken with possible suicidal/self-harming intent. Such overdoses should be reported regardless of sequelae.
- "Lack of efficacy" or "failure of expected pharmacological action" per se will not be reported as an AE or SAE. Such instances will be captured in the efficacy assessments. However, the signs, symptoms, and/or clinical sequelae resulting from lack of efficacy will be reported as AE or SAE if they fulfill the definition of an AE or SAE.
- The signs, symptoms, and/or clinical sequelae resulting from lack of efficacy will be reported as AE or SAE if they fulfill the definition of an AE or SAE. Also, "lack of efficacy" or "failure of expected pharmacological action" constitutes an AE or SAE.

Events NOT Meeting the AE Definition

- Any clinically significant abnormal laboratory findings or other abnormal safety

assessments which are associated with the underlying disease, unless judged by the investigator to be more severe than expected for the participant's condition.

- The disease/disorder being studied or expected progression, signs, or symptoms of the disease/disorder being studied, unless more severe than expected for the participant's condition.
- Medical or surgical procedure (e.g., endoscopy, appendectomy): the condition that leads to the procedure is the AE.
- Situations in which an untoward medical occurrence did not occur (social and/or convenience admission to a hospital).
- Anticipated day-to-day fluctuations of pre-existing disease(s) or condition(s) present or detected at the start of the study that do not worsen.

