9.2. Adverse Events

The definitions of an AE or SAE can be found in [Appendix 3](#).

The investigator and any designees are responsible for detecting, documenting, and reporting events that meet the definition of an AE or SAE and remain responsible for following up AEs that are serious, considered related to the study treatment or the study, or that caused the participant to discontinue study treatment (see Section 8).

Events should be reported as an AE or SAE according to the definitions in [Appendix 3](#).

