12.3.2. Definition of SAE

If an event is not an AE per definition above, then it cannot be an SAE even if serious conditions are met (e.g., hospitalization for signs/symptoms of the disease under study, death due to progression of disease).

A SAE is defined as any untoward medical occurrence that, at any dose:

a. Results in death

b. Is life-threatening

The term 'life-threatening' in the definition of 'serious' refers to an event in which the participant was at risk of death at the time of the event. It does not refer to an event, which hypothetically might have caused death, if it were more severe.

Requires inpatient hospitalization or prolongation of existing hospitalization

In general, hospitalization signifies that the participant has been detained (usually involving at least an overnight stay) at the hospital or emergency ward for observation and/or treatment that would not have been appropriate in the physician's office or outpatient setting. Complications that occur during hospitalization are AE. If a complication prolongs hospitalization or fulfills any other serious criteria, the event is serious. When in doubt as to whether "hospitalization" occurred or was necessary, the AE should be considered serious.

Hospitalization for elective treatment of a pre-existing condition that did not worsen from baseline is not considered an AE.

Results in persistent disability/incapacity

- The term disability means a substantial disruption of a person's ability to conduct normal life functions.
- This definition is not intended to include experiences of relatively minor medical significance such as uncomplicated headache, nausea, vomiting, diarrhea, influenza,

and accidental trauma (e.g., sprained ankle) which may interfere with or prevent everyday life functions but do not constitute a substantial disruption.

Is a congenital anomaly/birth defect

Other situations:

- Medical or scientific judgment should be exercised in deciding whether SAE reporting is appropriate in other situations such as important medical events that may not be immediately life-threatening or result in death or hospitalization but may jeopardize the participant or may require medical or surgical intervention to prevent one of the other outcomes listed in the above definition. These events should usually be considered serious.

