### **8.3. Adverse Events Analyses**

Adverse events will be coded using the Medical Dictionary for Regulatory Activities (MedDRA) coding dictionary.

Adverse events analyses including the analysis of adverse events (AEs), Serious (SAEs) and other significant AEs will be based on GSK Core Data Standards. The details of the planned displays are provided in [Appendix 10: List of Data Displays](#).

For the purpose of AE summaries and analysis, the investigator-reported AE details will be used, regardless of the adjudication outcome of the event.

See Section 14.4.1 for AE treatment-state definitions.

The adverse event safety analyses will be based on the Safety population, unless otherwise specified.

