**14.4.1.4. Study Phase for AE Data**

All AEs (non-serious AEs and serious AEs) will be collected and recorded on the eCRF from the start of treatment until the follow-up visit at the time points specified in the SoA from Section 14.2. Serious AEs assessed as related to study participation (e.g., study treatment, protocol-mandated procedures, invasive tests, or change in existing therapy) or related to a GSK product will be recorded on the eCRF from the time a participant consents to participate in the study up to and including any follow-up contact. AE of worsening of an on-going event will be counted once in a particular study phase.

Study Phase	Definition
Pre-treatment	
 
For subjects with a non-missing screen failure date, if AE onset is on or before the screen failure date: AE Start Date <math>\leq</math> Screen Failure Date
 
For randomized subjects with a missing treatment start date, all AEs are considered pre-treatment
 
For randomized subjects with a non-missing treatment start date, if AE onset date is before treatment start date: AE Start Date <math><</math> Treatment Start Date
 

Post-randomization	
If AE onset date or AE worsening date is on or after the randomization date  Randomization date <math>\leq</math> AE Start Date  Randomization date <math>\leq</math> AE Worsening Date  AE worsening during post-randomization will be defined relative to the maximum intensity of AE prior to randomization date.
 
AE worsening date is the first date in the post-randomization period, when AE intensity increased relative to the maximum intensity of the AE prior to randomization date.

Treatment emergent	
If AE onset date or AE worsening date is on or after treatment start date & on or before the last non-zero dose date plus 1 day.  Treatment Start Date <math>\leq</math> AE Start Date <math>\leq</math> Last Non-Zero Dose Date + 1 day  Treatment Start Date <math>\leq</math> AE Worsening Date <math>\leq</math> Last Non-Zero Dose Date + 1 day  AE worsening during treatment emergent period will be defined relative to the maximum intensity of AE prior to study treatment start date.
 
AE worsening date is the first date in the treatment emergent period, when AE intensity increased relative to the maximum intensity of the AE prior to study treatment start date.

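### Protocol 12.3.1 gives two opposite rules on whether lack of efficacy in itself is an adverse event, and neither document says which applies

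*Protocol*

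**What the plan says.** The conflict lies between two consecutive bullets of Protocol 12.3.1, in the list of events that meet the AE definition.

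- **Bullet A.** Lack of efficacy, or failure of the expected pharmacological effect, "per se will not be reported as an AE or SAE". It adds: "Such instances will be captured in the efficacy assessments".
- **Bullet B.** The same two terms, unqualified: each "constitutes an AE or SAE".
- **Common to both.** Signs, symptoms and "clinical sequelae resulting from lack of efficacy will be reported as AE or SAE if they fulfill the definition of an AE or SAE".

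Other sections depend on this definition. Protocol 9.2 sends investigators to Appendix 3: "Events should be reported as an AE or SAE according to the definitions in" that appendix. Protocol 12.3.2 makes SAE status follow from AE status: "If an event is not an AE per definition above, then it cannot be an SAE even if serious conditions are met".

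On the analysis side, SAP 8.3 states that "the investigator-reported AE details will be used". SAP 14.4.1.4 then assigns records to study phases by date. A record is treatment emergent if "AE onset date or AE worsening date is on or after treatment start date" and no later than one day after the last non-zero dose. Neither SAP section has a rule for records of lack of efficacy.

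**The concern.** An AE count needs one case definition, even when it is only described and not tested. Here the definition that sites must apply points both ways for one kind of case: an inadequate response with no reportable consequence. The design expects inadequate responders. Protocol 7.9 sets out a rescue algorithm, and Protocol 8.1 lists meeting its second step as a reason to stop study treatment.

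A site that follows bullet A leaves such a case out of the AE data. A site that follows bullet B enters it. A deviation review could fault neither. What is at stake is the comparability between sites of the AE counts, which belong to a stated safety endpoint (Protocol 4), and the clarity of the instruction to investigators.

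**Working it through.** There is no planned figure to reproduce. The check compares texts and then looks for a rule that decides between them.

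**Step 1: where the bullets agree and where they conflict**

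| Case | Bullet A | Bullet B | Conflict? |
|---|---|---|---|
| Lack of efficacy with signs, symptoms or sequelae that meet the AE definition | Report the consequence | Report the consequence, and the lack of efficacy is itself an AE or SAE | None on the consequence; yes on a separate entry for lack of efficacy |
| Lack of efficacy with no qualifying consequence | Do not report | It is an AE or SAE | Yes |

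The conflict is thus confined to an entry for lack of efficacy in itself.

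**Step 2: is there a deciding rule?**

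- Protocol 9.2 and 9.2.1 refer back to Appendix 3 and add no rule of their own.
- The list in 12.3.1 of events that do not meet the AE definition excludes laboratory abnormalities tied to the underlying disease. It also excludes the disease under study and its expected course. Both exclusions lapse if the finding is worse than expected for the participant. In this trial, inadequate response means low hemoglobin in anemia of CKD, so many such cases already fall under these exclusions. The list does not name lack of efficacy, whereas bullet B does, so it does not override bullet B.
- The overdose bullet in 12.3.1 follows the pattern of bullet A: its clinical consequences are reportable, but the overdose itself is not, except where self-harm is intended. This suggests that bullet A was meant, but does not say so.
- Protocol 12.3.2 passes the ambiguity on to SAE status. It does not resolve it.
- SAP 8.3, 14.4.1.4 and 14.6.4.3 contain no rule for these records.

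The surrounding text therefore leans toward bullet A and narrows the exposed cases, but nothing gives either bullet precedence.

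**Step 3: what a record would touch**

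- *Exposed:* the overall AE summaries and any lack-of-efficacy preferred-term row (SAP 8.3.2).
- *Common-AE displays:* these use a threshold of 5% in any arm. With the planned arms, 0.05 × 268 = 13.4 and 0.05 × 134 = 6.7. Such a term would enter only with at least 14 daprodustat or 7 epoetin alfa participants, if all planned participants are treated. These are entry thresholds, not expected counts.
- *Not exposed:* the primary analysis uses hemoglobin values (SAP 7.1.5.1). The principal secondary uses IV iron records (SAP 7.2.5.1). Time to rescue uses the treatment stop date with its own reason and subreason (SAP 14.6.3.3). MACE uses adjudicated events (SAP 8.2).

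**Step 4: size**

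The documents give no rate of inadequate response, no number of AE records for lack of efficacy, and no indication of which bullet sites follow. The size cannot be computed, and zero is possible.

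**The case against.** The best case on the other side is that this is leftover template wording with little consequence. The exclusions for the underlying disease and the overdose wording both favour bullet A, and an investigator might well read the section that way. The protocol also refers sites to the Study Reference Manual, which is not available here and may give clarifying instructions. Any lack-of-efficacy record would already be visible, because preferred-term tables and listings linking terms to subjects and verbatim text are planned.

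Much of this stands. It limits the number of exposed cases, and it means that divergence between sites is possible rather than shown. It does not remove the contradiction: the protocol is the operative text, and a reader cannot tell from it which bullet is the leftover.

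A reader might infer three stronger things that the documents do not support:

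- **That SAE counts or AEs leading to discontinuation are materially distorted.** A serious consequence would normally be reportable under either bullet. Rescue stops have their own eCRF form and stop reason. No section shows that a lack-of-efficacy entry would be recorded as an AE that led to discontinuation.
- **That one arm is favoured.** The trial is double-blind (Protocol 7.4), so inconsistent reporting alone gives no reason to expect this. AE data are summarized descriptively (Protocol 10.3.2). The relative risks with confidence intervals in SAP 8.3.1 and 8.3.2 are not formal tests.
- **That showing AE counts with and without the flagged records would repair comparability.** A flag finds only what was entered. It cannot reveal cases left out by sites that follow bullet A.

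**Conclusion.** The contradiction is real, literal and in the current protocol text. It concerns only lack of efficacy in itself. Its consequence is that the same case can be reported at one site and not at another, mainly affecting counts of non-serious AEs. No efficacy conclusion and no adjudicated cardiovascular result depends on it.

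This rests on two assumptions: that no instruction outside the two documents has already told sites which bullet to follow, and that some inadequate responses occur without a reportable consequence and outside the exclusions for the underlying disease. If either fails, the practical effect may vanish, but the text should still be corrected. It is a modest point that merits correction because the definition is wrong as written and cheap to repair.

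**What to change.** Reconcile the two bullets of Protocol 12.3.1 into one rule and notify all sites. Deleting bullet B is the simplest course. It agrees with bullet A's statement that such cases belong to the efficacy data, and it removes no duty to report sequelae, because that sentence stands in both bullets.

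If data collection has ended, a change to the protocol can no longer help. In that case, use the listing of system organ class, preferred term and verbatim text already planned in SAP 8.3.2 to identify any AE or SAE record of lack of efficacy in itself before unblinding. Note those records when AE counts are reported, and state that cases left unreported cannot be recovered.

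The cost is a short amendment or clarification, with ethics committee handling as applicable (Protocol 12.2.1), a notice to sites and, where needed, a blinded look at a listing already planned. The downside is that reporting may differ before and after the clarification. The listing can show this only in part, for the same reason that unreported cases stay hidden.
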